## 4 STUDY POPULATION

### 4.1 Inclusion Criteria

1. Male and females 12 to 17 years (inclusive) of age at the time of informed consent.
2. Have a diagnosis of episodic migraine with or without aura according to International Classification of Headache Disorders-3rd edition, beta version (ICHD-IIIB, 1.2.1 or 1.1) criteria for at least 1 year prior to the screening/enrollment visit.
3. Experienced migraine attacks of moderate-to-severe intensity and typically lasting  $\geq$  3 hours untreated, occurring at a frequency of  $\geq$  2 to  $\leq$  14 attacks per month for the past 6 months prior to the screening/enrollment visit.
4. Subject's parent or legal guardian must be willing to sign a copy of informed consent form (ICF) as well as documentation for Written Authorization for Use and Release of Health and Research Study Information, after the nature and risks of study participation have been fully explained.
5. Subjects also must be willing to provide minor assent according to the state law and Institutional Review Board (IRB) requirements, after the nature and risks of study participation have been fully explained.
6. Subjects must have a verified airflow through both nostrils and an ability to close the soft palate.
7. Subjects must demonstrate the ability to use the Breath Powered delivery device correctly.
8. Able and willing to read and comprehend written instructions and complete the diary. Subjects with  $\geq$  75% diary data entry for Migraine Attack 1 are eligible to be randomized.
9. Female patients who are of childbearing potential (post-menarche) must:
  - a. agree to practice a medically acceptable method of birth control during the entire study duration (oral contraceptive tablets, hormonal implant device, hormone patch, intrauterine device, diaphragm and contraceptive cream or foam, condom with spermicide, or abstinence) or be surgically sterile, and
  - b. have a negative urine pregnancy test at screening/enrollment and baseline visits.

### 4.2 Exclusion Criteria

1. Subjects who weigh less than 30 kg.

---

- 2. Subjects with a body mass index (BMI) of more than 40.
- 3. Subjects with  $\geq 15$  headache days per month in total (migraine, probable migraine, or tension-type).
- 4. Subjects with the following headache types: retinal [ICHD-IIIB 1.2.4], with brainstem aura [ICHD-IIIB 1.2.2], hemiplegic [ICHD-IIIB 1.2.3)], status migrainosus [ICHD-IIIB 1.4.1], other forms of complicated migraine, or secondary headaches.
- 5. Subjects who have not responded to an adequate dose and appropriate duration of treatment with 2 or more triptans.
- 6. Current use of medication for migraine prophylaxis that has not been stable or requires dose adjustment within 7 days prior to the screening/enrollment visit or if a dose adjustment is expected during the study.
- 7. Received chronic opioid therapy for more than 3 consecutive days within the 30 days prior to the screening/enrollment visit.
- 8. Current treatment with monoamine oxidase A (MAO-A) inhibitors or use within 4 weeks before the screening/enrollment visit.
- 9. Subjects with known nasal obstruction, current uncontrolled nasopharyngeal illness, or known velum insufficiency (i.e., a cleft palate and/or structural abnormalities in the soft palate and nasopharynx) which may interfere with the proper use of study medication.
- 10. History of clinically significant abnormality in electrocardiogram.
- 11. History or current symptoms or signs of ischemic cardiac, cerebrovascular or peripheral vascular syndrome.
- 12. Uncontrolled hypertension defined as systolic or diastolic blood pressure that exceeds the 90th percentile for age and height ([Appendix 1](#)).
- 13. Any disease or condition which in the opinion of the investigator would contraindicate study participation such as a history of coronary artery disease, coronary vasospasm or a cardiac accessory conduction pathway disorder; a history of stroke, transient ischemic attack, or hemiplegic or basilar migraine; peripheral vascular disease; ischemic bowel disease; uncontrolled hypertension; severe hepatic impairment; epilepsy; drug or alcohol abuse; any systemic disease, neurological or psychiatric condition.
- 14. Subjects who fail urine drug screen test at the screening/enrollment visit.
- 15. Current suicide risk, as evidenced by any of the following:
  - a. It is the judgment of the investigator that the subject may be at risk for suicide.

---

- b. The subject is rated a “yes” to question 4 or question 5 on the C-SSRS at screening/enrollment or randomization visit, and the most recent episode occurred within the past 6 months prior to the screening/enrollment visit.
- c. The subject has attempted suicide within the past 12 months prior to the screening/enrollment visit.

16. Hypersensitivity or intolerance to sumatriptan, any of its components, or sulphonamides.

17. Subjects whose conditions in the investigator’s opinion may put the subject at significant safety risk or confound the study results. This include subjects who in the investigator’s opinion should not be enrolled in the study due to the risks described in Warnings and Precautions or Contraindications sections of the ONZETRA Xsail Prescribing Information.

18. Have taken any investigational medication within 4 weeks before the screening/enrollment visit, or are scheduled to receive an investigational drug, other than sumatriptan for this study, while participating in the study.

19. Females who are pregnant or breast-feeding.

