### **6.2.6        Columbia Suicide Severity Rating Scale (C-SSRS)**

The C-SSRS (Appendix 3) is a low-burden measure of the spectrum of suicidal ideation and behavior that was developed by Columbia University researchers for the National Institute of Mental Health Treatment of Adolescent Suicide Attempters Study to assess severity and track suicidal events through any treatment. It is a clinical interview providing a summary of both ideation and behavior that can be administered during any evaluation or risk assessment to identify the level and type of suicidality present. The C-SSRS can also be used during treatment to monitor for clinical worsening.

The C-SSRS evaluation will be performed at all clinic visits (Visit 1 ['baseline/screening' version], Visit 2 and Visit 3 ['since last visit' version]).

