### **6.3.1.2 Visit 2 (Randomization)**

The following procedures should be performed at Visit 2

1. Review and record medical and migraine history
2. Review and record prior and concomitant medications
3. Review eligibility (inclusion/exclusion criteria)
4. Collect urine specimen for drug screen
5. Urine pregnancy test (for females of childbearing potential only)
6. Administer the C-SSRS
7. Train subject on the use of study medication
8. Query subject on any adverse events
9. Perform nasal examination
10. Review diary and return to subject
11. Randomization
12. Access IWRs to obtain assigned kit number for study medication
13. Dispense study medication

Subjects will be instructed to treat one migraine headache of moderate to severe intensity in the subsequent 12 weeks (84 days) with the study medication and to respond to questions on the study diary. Diary should be used before taking the study treatment and at 15, 30, 60, 120 min, 3 hours, 4 hours, and 24 hours after dosing. A monthly phone call to the subject or their parent/legal guardian will be placed by site personnel to inquire about any adverse events or to answer study question.

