**Appendix 2: Columbia Suicide Severity Rating Scale (C-SSRS)**

## COLUMBIA-SUICIDE SEVERITY RATING SCALE

### Visit 2 and Visit 3 Exit/Early Termination Visit

SITE NUMBER	PATIENT NUMBER	PATIENT INITIALS	VISIT NUMBER	VISIT DATE	EXAMINER INITIALS

Since Last Visit

Version 1/14/09

**Posner, K.; Brent, D.; Lucas, C.; Gould, M.; Stanley, B.; Brown, G.; Fisher, P.; Zelazny, J.; Burke, A.; Oquendo, M.; Mann, J.**

Disclaimer:

*This scale is intended to be used by individuals who have received training in its administration. The questions contained in the Columbia-Suicide Severity Rating Scale are suggested probes. Ultimately, the determination of the presence of suicidal ideation or behavior depends on the judgment of the individual administering the scale.*

Definitions of behavioral suicidal events in this scale are based on those used in **The Columbia Suicide History Form**, developed by [name] and [name], Conte Center for the Neuroscience of Mental Disorders (CCNMD), New York State Psychiatric Institute, [name]. (Oquendo M. A., Halberstam B. & Mann J. J., Risk factors for suicidal behavior: utility and limitations of research instruments. In M.B. First [Ed.] Standardized Evaluation in Clinical Practice, pp. 103 -130, 2003.)

For reprints of the C-SSRS contact [name]., New York State Psychiatric Institute, [name]; inquiries and training requirements contact [contact]

© 2008 The Research Foundation for Mental Hygiene, Inc.

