Have you made a suicide attempt? Have you done anything to harm yourself? Have you done anything dangerous where you could have died? What did you do? Did you _____ as a way to end your life? Did you want to die (even a little) when you _____? Were you trying to end your life when you _____? Or did you think it was possible you could have died from _____? Or did you do it purely for other reasons / without ANY intention of killing yourself (like to relieve stress, feel better, get sympathy, or get something else to happen)? (Self-Injurious Behavior without suicidal intent) If yes, describe:		Yes  No   Total # of interrupted <hr/>
Has subject engaged in Non-Suicidal Self-Injurious Behavior?		Yes  No   Total # of aborted <hr/>
Interrupted Attempt: When the person is interrupted (by an outside circumstance) from starting the potentially self-injurious act ( if not for that, actual attempt would have occurred ). Overdose: Person has pills in hand but is stopped from ingesting. Once they ingest any pills, this becomes an attempt rather than an interrupted attempt. Shooting: Person has gun pointed toward self, gun is taken away by someone else, or is somehow prevented from pulling trigger. Once they pull the trigger, even if the gun fails to fire, it is an attempt. Jumping: Person is poised to jump, is grabbed and taken down from ledge. Hanging: Person has noose around neck but has not yet started to hang - is stopped from doing so. Has there been a time when you started to do something to end your life but someone or something stopped you before you actually did anything? If yes, describe:		Yes  No   Total # of interrupted <hr/>
Aborted Attempt: When person begins to take steps toward making a suicide attempt, but stops themselves before they actually have engaged in any self-destructive behavior. Examples are similar to interrupted attempts, except that the individual stops him/herself, instead of being stopped by something else. Has there been a time when you started to do something to try to end your life but you stopped yourself before you actually did anything? If yes, describe:		Yes  No   Total # of aborted <hr/>

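### Exclusion 15b names the randomization visit but counts only episodes before screening, so new suicidal ideation in the run-in does not trigger it; 15c likewise misses an attempt between Visits 1 and 2

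*Combined protocol and SAP*

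**What the plan says.** Protocol Section 4.2, exclusion 15, opens with "Current suicide risk, as evidenced by any of the following" and gives three routes to exclusion:

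- **15a**, with no time window: "It is the judgment of the investigator that the subject may be at risk for suicide".
- **15b**, a yes rating to question 4 (ideation with some intent to act) or question 5 (plan and intent) "on the C-SSRS at screening/enrollment or randomization visit, and the most recent episode occurred within the past 6 months prior to the screening/enrollment visit".
- **15c**, which names no assessment visit: "The subject has attempted suicide within the past 12 months prior to the screening/enrollment visit".

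Section 6.2.6 assigns the baseline/screening form to Visit 1 and a different form to the later visits: "Visit 2 and Visit 3 ['since last visit' version". The form in Appendix 2 is marked "Visit 2 and Visit 3 Exit/Early Termination Visit", its answer columns refer to the time since the last visit, and among its items is "Have you made a suicide attempt".

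Section 6.3.1.2 lists the Visit 2 procedures. Eligibility review is step 3, "Administer the C-SSRS" is step 6 and randomization is step 11. Table 1, note 2, requires a completed eligibility form before randomization. Section 6.3.1.1 has that form sent to the Medical Monitor for approval once the run-in attack has been treated.

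**The concern.** 15b is meant to operate at two visits. At the second of them, the instrument and the time condition look at different periods: the form asks what has happened since Visit 1, and the criterion counts only what happened before Visit 1. The clause can hardly ever be satisfied by what is found at Visit 2.

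The result runs against the purpose of a rule about current risk. Ideation with intent 5 months before screening excludes an adolescent automatically. The same ideation in the week before randomization, just before possible exposure to active drug, does not. An attempt during the run-in is treated the same way under 15c.

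At stake is uniform and auditable handling of suicidality in minors at approximately 30 centers. The treatment comparison is not at stake, because the rule acts before randomization and applies to both arms alike.

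**Working it through.** The plan gives no figure on this point to reproduce. The check sets the time windows side by side, with Visit 1 as day 0 and Visit 2 as day V.

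**1. Windows**

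| Source | Period covered |
|---|---|
| 15b time condition | 6 months before day 0, up to day 0 |
| 15c | 12 months before day 0, up to day 0 |
| Visit 2 C-SSRS (since last visit) | after day 0, up to day V |

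Counting the days after day 0 and up to V that fall inside the 15b or 15c window gives 0 for every V tried (7, 50, 94, 98, 178 and 182). There is one small qualification. Table 1 lets Visit 1 run from Day -3 to 1. If the first C-SSRS is done at the start of that window and the visit is dated at its end, the overlap could reach 4 days at most.

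**2. Length of the uncovered period (Visit 1 to Visit 2)**

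Inputs: a run-in of up to 12 weeks, or 84 days (Sections 3 and 6.3.1.1); a possible further 12 weeks with sponsor approval (Section 4.3 and the Table 1 note); Visit 2 at 10 ± 4 days after Attack 1 (Table 1).

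- Longest without extension: 84 + 10 + 4 = 98 days = 14 weeks.
- Longest with extension: 168 + 10 + 4 = 182 days = 26 weeks.

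These are upper limits. As an illustration, assume that attacks occur at random at the 2 to 14 per month of inclusion 3, that a month has 30 days, and that the first attack is treated. The mean period is then 30/2 + 10 = 25 days at the low frequency and 30/14 + 10 = 12.1 days at the high one, or roughly 2 to 4 weeks.

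**3. What the criteria require, case by case**

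| Event | As written | With both windows extended to randomization |
|---|---|---|
| Question 4/5 ideation 5 months before screening, rated yes at Visit 1 | Excluded by 15b | Excluded by 15b |
| Question 4/5 ideation in the week before Visit 2, rated yes at Visit 2 | Not excluded by 15b | Excluded by 15b |
| Attempt within the 12 months before screening | Excluded by 15c | Excluded by 15c |
| Attempt between Visits 1 and 2 | Not excluded by 15c | Excluded by 15c |

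With the extension, every day from 1 to V is covered by construction.

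**4. Number of subjects**

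Expected cases = (subjects assessed at Visit 2) × (rate of such events between the visits). The documents do not give the rate. Nor is the first factor 236, which is the number randomized and treated in Section 8.4. Everyone assessed at Visit 2 is at issue, a number somewhere between 236 and the 420 entering the run-in. No case count can be derived.

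**The case against.** The strongest reply is that the event would be detected and could be acted on.

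- The Visit 2 C-SSRS is listed before randomization, so the finding is known in time.
- 15a has no window and becomes an exclusion once the investigator judges that risk may exist. A yes to question 4 or 5 means intent, which is hard to judge as no risk.
- Exclusions 13 and 17 and the discontinuation provision in Section 4.3 give further grounds.
- A run-in attempt that was life-threatening, led to hospitalization or was otherwise medically important would be a serious adverse event, telephoned to the Medical Monitor within 24 hours (Sections 6.2.1.2 and 6.2.1.3).
- A site reading 15b for its purpose would probably exclude, since the literal reading leaves the mention of the randomization visit idle.

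Most of this stands, and it limits the severity. A reader might infer that adolescents with new suicidal intent would be randomized, or that the protocol has no safeguard at Visit 2. The documents do not support either.

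The reply does not restore the mandatory trigger. 15a, 13 and 17 depend on opinion, and Section 4.3 is permissive. 15b and 15c stand beside 15a as criteria that do not depend on the investigator's view of risk. Nor can the Medical Monitor's approval be counted as a sure check: Section 6.3.1.1 places it after the run-in attack, Section 6.3.1.2 lists no Medical Monitor step, and neither says that approval follows the Visit 2 C-SSRS. It would be equally wrong to conclude that the Medical Monitor never sees the result; the documents leave this open.

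A reader might also take the screening anchor as a deliberate choice, or argue that the protocol reaches to randomization whenever it means to. Neither inference is safe. The look-back for investigational drugs is anchored at screening in exclusion 18 and at randomization in Section 5.4, which points to uneven drafting.

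**Conclusion.** The point holds as a wording error in a mandatory safety rule. 15b has essentially no effect at one of its two named visits: the overlap is 0 days, or at most 4 on the widest reading of the Visit 1 window. 15c does not contradict itself, but it leaves the same period uncovered. That period is Visit 1 to Visit 2, at most about 14 weeks, or 26 with an approved extension.

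The conclusion rests on the literal text of 15b and 15c and on the since-last-visit form being used at Visit 2, as Section 6.2.6 and Appendix 2 both state. The limits of 14 and 26 weeks follow from the protocol's own timings; the typical duration of 2 to 4 weeks depends on the assumed attack pattern.

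What is lost is the automatic exclusion, with discretionary routes still in place. Without an event rate, no number of affected or wrongly randomized subjects should be stated. Severity is minor to should-fix.

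**What to change.** Keep the 6-month and 12-month look-backs and add the run-in to each:

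- **15b**, time condition: *within the 6 months before the screening/enrollment visit or at any time since, up to randomization*.
- **15c**: *within the 12 months before the screening/enrollment visit or at any time since, up to randomization*.

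Carry both changes to the protocol eligibility form.

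The cost is one phrase in each of two criteria and the matching lines on the form. No visit, test or questionnaire is added, because the Visit 2 C-SSRS already collects ideation and attempts and is listed before randomization. The downside is possibly a few more exclusions at Visit 2, some of which 15a would have made anyway.

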#### **4.3            Subject Withdrawal from the Study**

Subjects and their parent/legal guardian will be advised verbally and in the written ICF that they have the right to withdraw from the study at any time without prejudice or loss of benefits to which they are otherwise entitled. The investigator or sponsor may discontinue a subject from the study in the event of an intercurrent illness, adverse event, other reasons concerning the health or well-being of the subject, or in the case of lack of cooperation, non-compliance, protocol violation, or other administrative reasons. Subjects who are placebo responders (defined as subjects who are headache pain free 2 hours post treatment of Migraine Attack 1) will be withdrawn from the study and procedures specified at the exit/early termination visit (Visit 3) will be performed. Subjects who do not have a migraine attack within 12 weeks of the screening/enrollment visit (single-blind phase) or randomization (double-blind treatment phase) may be granted another 12 weeks in each period based on sponsor approval. If a subject does not return for a scheduled visit, every effort should be made to contact the subject. Regardless of the circumstance, every effort should be made to document subject outcome, if possible. The investigator should inquire about the reason for withdrawal, request the subject/parent/legal guardian to return all unused investigational product (IP), and follow-up with the subject and

---

their parent/legal guardian regarding any unresolved adverse events.

If the subject and their parent/legal guardian withdraws from the study, and consent is withdrawn for disclosure of future information, no further evaluations should be performed, and no additional data should be collected. The sponsor may retain and continue to use any data collected before such withdrawal of consent. Subjects who withdraw from the study will not be replaced.

## 5 STUDY TREATMENTS

### 5.1 Treatments Administered

All medication used in this study will be prepared, packaged, and labeled in accordance with Good Manufacturing Practice (GMP) guidelines, International Conference on Harmonisation (ICH) Good Clinical Practice (GCP) guidelines, and applicable laws and regulations.

#### 5.1.1 Description and Composition of Study Medications

Clinical study medication will be provided in individual cartons containing one dose. Each carton/dose will consist of one ONZETRA Xsail reusable device body, and one foil laminated pouch containing 2 single-use nosepieces, equivalent to one dose of study medication. Each nosepiece will contain sumatriptan succinate or placebo (lactose monohydrate) dry powder in a clear, size 3, hydroxypropyl methylcellulose (HPMC) inhalation capsule printed with black ink on the cap.

Two different strengths of study medication will be provided as follows:

- AVP-825 22 mg of sumatriptan; 2 nosepieces in a pouch with each nosepiece/capsule containing 11 mg sumatriptan (equivalent to 15.4 mg of sumatriptan succinate).
- AVP-825 Placebo; 2 nosepieces in a pouch with each nosepiece/capsule containing lactose monohydrate.

The composition of each nosepiece of the IP is shown in [Table 3](#).

**Table 3 Composition of One Capsule/Nosepiece**

Ingredient	AVP-825 11 mg (mg)	Placebo (mg)
Sumatriptan succinate, USP dry powder	15.4	0
Lactose monohydrate, NF dry powder	0	30.0 
HPMC inhalation capsule	45	45

HPMC = Hydroxypropyl methylcellulose; NF = National Formulary; USP = United States Pharmacopoeia

 Volume of 30 mg of lactose monohydrate is equivalent to the volume of 15.4 mg of sumatriptan succinate; volume of powder in a clear capsule shell is critical for blinding purpose

Demonstration kits will be provided for training purposes. The demonstration kit will be clearly marked with the ONZETRA Xsail name and ‘demonstration kit contains no medication’. The kit

---

will consist of the reusable device body (the same device body as in the study medication kit but with a different label) and one foil laminated pouch containing 2 single-use nosepieces with the empty capsules marked with 'demo' on one side of the capsule.

### **5.1.2 Packaging**

The IP will be supplied as a blinded, pre-labeled, individually packaged drug device combination product kit. Each kit will contain a reusable device body, one pouch containing 2 nosepieces of active study medication or 2 nosepieces of placebo, and instructions for use.

